Appendix 1. Impact of Event Scale Revised (IES-R)

Permission from [name] by [name] MS pending.

(Read the following statement to the *participant*): I really appreciate your help with these surveys. I want to ask about something else now. The following is a list of difficulties people sometimes have after stressful life events. I will read each item, and then ask you to indicate how distressing each difficulty has been for you during the past 7 days with respect to your experience with your loved one’s ICU stay. How much were you distressed or bothered by these difficulties? In the questions, the word “it” refers to your experience with your loved one’s ICU stay.

1. Any reminder brought back feelings about it.	 1 Not at all  2 A little Bit  3 Moderately  4 Quite a bit  5 Extremely
2. I had trouble staying asleep.	 1 Not at all  2 A little Bit  3 Moderately  4 Quite a bit  5 Extremely
3. Other things kept making me think about it.	 1 Not at all  2 A little Bit  3 Moderately  4 Quite a bit  5 Extremely
4. I felt irritable and angry.	 1 Not at all  2 A little Bit  3 Moderately  4 Quite a bit  5 Extremely
5. I avoided letting myself get upset when I thought about it or was reminded of it.	 1 Not at all  2 A little Bit  3 Moderately  4 Quite a bit  5 Extremely
6. I thought about it when I didn’t mean to.	 1 Not at all  2 A little Bit  3 Moderately  4 Quite a bit  5 Extremely
7. I felt as if it hadn’t happened or wasn’t real.	 1 Not at all  2 A little Bit  3 Moderately  4 Quite a bit  5 Extremely

8. I stayed away from reminders of it.	 1 Not at all  2 A little Bit  3 Moderately  4 Quite a bit  5 Extremely
9. Pictures about it popped into my mind.	 1 Not at all  2 A little Bit  3 Moderately  4 Quite a bit  5 Extremely
10. I was jumpy and easily startled.	 1 Not at all  2 A little Bit  3 Moderately  4 Quite a bit  5 Extremely
11. I tried not to think about it.	 1 Not at all  2 A little Bit  3 Moderately  4 Quite a bit  5 Extremely
12. I was aware that I still had a lot of feelings about it, but I didn't deal with them.	 1 Not at all  2 A little Bit  3 Moderately  4 Quite a bit  5 Extremely
13. My feelings about it were kind of numb.	 1 Not at all  2 A little Bit  3 Moderately  4 Quite a bit  5 Extremely
14. I found myself acting or feeling like I was back at that time.	 1 Not at all  2 A little Bit  3 Moderately  4 Quite a bit  5 Extremely
15. I had trouble falling asleep.	 1 Not at all  2 A little Bit  3 Moderately  4 Quite a bit  5 Extremely
16. I had waves of strong feelings about it.	 1 Not at all  2 A little Bit  3 Moderately  4 Quite a bit  5 Extremely
17. I tried to remove it from my memory.	 1 Not at all  2 A little Bit  3 Moderately  4 Quite a bit  5 Extremely

18. I had trouble concentrating.	 1 Not at all  2 A little Bit  3 Moderately  4 Quite a bit  5 Extremely
19. Reminders of it caused me to have physical reactions, such as sweating, trouble breathing, nausea, or a pounding heart.	 1 Not at all  2 A little Bit  3 Moderately  4 Quite a bit  5 Extremely
20. I had dreams about it.	 1 Not at all  2 A little Bit  3 Moderately  4 Quite a bit  5 Extremely
21. I felt watchful and on guard.	 1 Not at all  2 A little Bit  3 Moderately  4 Quite a bit  5 Extremely
22. I tried not to talk about it.	 1 Not at all  2 A little Bit  3 Moderately  4 Quite a bit  5 Extremely

Hospital Anxiety and Depression Scale (HADS) License from GL Assessment pending.

Record responses directly on licensed copy of instrument from Nfer Nelson, UK & include with CRF

(Read the following introduction to the participant): I am now going to ask some different questions. Doctors are aware that emotions play an important part in most illnesses. This questionnaire is designed to help us to know how you feel. I will read each item with the possible responses. Please respond with the reply that comes closest to how you have been feeling in the past week. Don't take too long over your replies: your immediate reaction to each item will probably be more accurate than a long, thought out response.

1. I feel tense or 'wound up'
	
₁ Most of the time ₂ A lot of the time ₃ From time to time, occasionally ₄ Not at all

2. I still enjoy the things I used to enjoy
	
₁ Definitely as much ₂ Not quite so much ₃ Only a little ₄ Hardly at all


3. I get a sort of frightened feeling as if something awful is about to happen
	
₁ Very definitely and quite badly ₂ Yes, but not too badly ₃ A little, but it doesn't worry me ₄ Not at all

4. I can laugh and see the funny side of things
	
₁ As much as I always could ₂ Not quite so much now ₃ Definitely not so much now ₄ Not at all

5. Worrying thoughts go through my mind
	
₁ A great deal of the time ₂ A lot of the time ₃ From time to time but not too often ₄ Only occasionally

6. I feel cheerful
	
₁ Not at all ₂ Not often ₃ Sometimes ₄ Most of the time

7. I can sit at ease and feel relaxed	 ₁ Not at all  ₂ Not often  ₃ Sometimes  ₄ Most of the time
8. I feel as if I am slowed down	 ₁ Nearly all the time  ₂ Very often  ₃ Sometimes  ₄ Not at all
9. I get a sort of frightened feeling like 'butterflies' in the stomach	 ₁ Not at all  ₂ Occasionally  ₃ Quite often  ₄ Very often
10. I have lost interest in my appearance	 ₁ Definitely  ₂ I don't take so much care as I should  ₃ I may not take quite as much care  ₄ I take just as much care as ever
11. I feel restless, as if I have to be on the move	 ₁ Very much indeed  ₂ Quite a lot  ₃ Not very much  ₄ Not at all
12. I look forward with enjoyment to things	 ₁ As much as I ever did  ₂ Rather less than I used to  ₃ Definitely less than I used to  ₄ Hardly at all
13. I get sudden feelings of panic	 ₁ Very often indeed  ₂ Quite often  ₃ Not very often  ₄ Not at all
14. I can enjoy a good book or radio or TV program	 ₁ Often  ₂ Sometimes  ₃ Not often  ₄ Very Seldom

Coping with Stress (Brief COPE)

	I haven't been doing this at all	I've been doing this a little bit	I've been doing this a medium amount	I've been doing this a lot
1. I've been turning to work or other activities to take my mind off of things	1	2	3	4
2. I've been concentrating my efforts on doing something about the situation I'm in.	1	2	3	4
3. I've been saying to myself "this isn't real."	1	2	3	4
4. I've been using alcohol or other drugs to make myself feel better.	1	2	3	4
5. I've been getting emotional support from others.	1	2	3	4
6. I've been giving up trying to deal with it.	1	2	3	4
7. I've been taking action to try to make the situation better.	1	2	3	4
8. I've been refusing to believe that it has happened.	1	2	3	4
9. I've been saying things to let my unpleasant feelings escape.	1	2	3	4
10. I've been getting help and advice from other people.	1	2	3	4
11. I've been using alcohol or other drugs to help me get through it.	1	2	3	4
12. I've been trying to see it in a different light, to make it seem more positive.	1	2	3	4
13. I've been criticizing myself.	1	2	3	4
14. I've been trying to come up with a strategy about what to do.	1	2	3	4
15. I've been getting comfort and understanding from someone.	1	2	3	4
16. I've been giving up the attempt to cope.	1	2	3	4
17. I've been looking for something good in what is happening.	1	2	3	4
18. I've been making jokes about it.	1	2	3	4
19. I've been doing something to think about it less, such as going to movies, watching TV, reading, daydreaming, sleeping, or shopping.	1	2	3	4

20. I've been accepting the reality of the fact that it has happened.	1	2	3	4
21. I've been expressing my negative feelings.	1	2	3	4
22. I've been trying to find comfort in my religion or spiritual beliefs.	1	2	3	4
23. I've been trying to get advice or help from other people about what to do.	1	2	3	4
24. I've been learning to live with it.	1	2	3	4
25. I've been thinking hard about what steps to take.	1	2	3	4
26. I've been blaming myself for things that happened.	1	2	3	4
27. I've been praying or meditating	1	2	3	4
28. I've been making fun of the situation	1	2	3	4

Appendix 2. Post Traumatic Growth Inventory

Instructions: Please indicate for each of the statements below the degree to which this change occurred in your life as a result of your crisis, using the following scale.

	I did not experience this change as a result of my crisis	I experienced this change to a very small degree as a result of my crisis	I experienced this change to a small degree as a result of my crisis	I experienced this change to a moderate degree as a result of my crisis	I experienced this change to a great degree as a result of my crisis	I experienced this change to a very great degree as a result of my crisis
My priorities about what is important in life	0	1	2	3	4	5
An appreciation for the value of my own life	0	1	2	3	4	5
I developed new interests	0	1	2	3	4	5
A feeling of self-reliance	0	1	2	3	4	5
A better understanding of spiritual matters	0	1	2	3	4	5
Knowing that I can count on people in times of trouble	0	1	2	3	4	5
I established a new path for my life	0	1	2	3	4	5
A sense of closeness with others	0	1	2	3	4	5
A willingness to express my emotions	0	1	2	3	4	5
Knowing I can handle difficulties	0	1	2	3	4	5
I'm able to do better things with my life	0	1	2	3	4	5

	I did not experience this change as a result of my crisis	I experienced this change to a very small degree as a result of my crisis	I experienced this change to a small degree as a result of my crisis	I experienced this change to a moderate degree as a result of my	I experienced this change to a great degree as a result of my crisis	I experienced this change to a very great degree as a result of my crisis
Being able to accept the way things work out	0	1	2	3	4	5
Appreciating each day	0	1	2	3	4	5
New opportunities are available which wouldn't have been	0	1	2	3	4	5
Having compassion for others	0	1	2	3	4	5
Putting effort into my relationships	0	1	2	3	4	5
I'm more likely to try to change things which need changing	0	1	2	3	4	5
I have a stronger religious faith	0	1	2	3	4	5
I discovered that I'm stronger than I thought I was	0	1	2	3	4	5
I learned a great deal about how wonderful people are	0	1	2	3	4	5
I accept needing others	0	1	2	3	4	5

Appendix 3. Essay Evaluation Measure

Instructions: Please answer the following questions about your essay using the scale provided.

	Not at All	Low	Slightly	Neutral	Moderately	Very	A Great Deal
How personal was the essay that you wrote today?	0	1	2	3	4	5	6
How much did you reveal your emotions in what you wrote today?	0	1	2	3	4	5	6
Have much of what you wrote today have you shared with/told others?	0	1	2	3	4	5	6

Appendix 4.

Groningen Activity Restriction Scale (GARS)

The following questions refer to daily activities which should be performed frequently. In each question it is asked whether you *are able to perform* the activity at this moment. It is not intended to assess whether you are actually performing the activities, but if you can do them if necessary.

Response categories for each item

1. Yes, I can do it fully independently without any difficulty
2. Yes, I can do it fully independently but with some difficulty
3. Yes, I can do it fully independently but with great difficulty
4. No, I cannot do it fully independently, I can only do it with someone’s help

GARS items

1. Can you, fully independently, dress yourself?
2. Can you, fully independently, get in and out of bed?
3. Can you, fully independently, stand up from sitting in a chair?
4. Can you, fully independently, wash your face and hands?
5. Can you, fully independently, wash and dry your whole body?
6. Can you, fully independently, get on and off the toilet?
7. Can you, fully independently, feed yourself?
8. Can you, fully independently, get around in the house (if necessary with a cane or walker)?
9. Can you, fully independently, go up and down the stairs?
10. Can you, fully independently, walk outdoors (if necessary with a cane or walker)?
11. Can you, fully independently, take care of your feet and toenails?
12. Can you, fully independently, prepare breakfast or lunch?
13. Can you, fully independently, prepare dinner?
14. Can you, fully independently, do “light” household activities (for example, dusting and tidying up)?
15. Can you, fully independently, do “heavy” household activities (for example mopping, cleaning the windows, and vacuuming)?
16. Can you, fully independently, wash and iron your clothes?
17. Can you, fully independently, make the beds?
18. Can you, fully independently, do the shopping?

Activity Restriction Scale (ARS)

“Please tell me how much you have restricted your activities in each of the following areas due to the care you are providing to your loved one:	
1. Care of yourself?	 1 Not restricted at all  2 Slightly restricted  3 Moderately restricted  4 Greatly restricted
2. Caring for others?	 1 Not restricted at all  2 Slightly restricted  3 Moderately restricted  4 Greatly restricted

3. Eating habits?	 1 Not restricted at all  2 Slightly restricted  3 Moderately restricted  4 Greatly restricted
4. Sleeping habits?	 1 Not restricted at all  2 Slightly restricted  3 Moderately restricted  4 Greatly restricted
5. Doing household chores?	 1 Not restricted at all  2 Slightly restricted  3 Moderately restricted  4 Greatly restricted
6. Going shopping for him/herself	 1 Not restricted at all  2 Slightly restricted  3 Moderately restricted  4 Greatly restricted
7. Visiting friends?	 1 Not restricted at all  2 Slightly restricted  3 Moderately restricted  4 Greatly restricted
8. Working on hobbies?	 1 Not restricted at all  2 Slightly restricted  3 Moderately restricted  4 Greatly restricted
9. Sports and recreation?	 1 Not restricted at all  2 Slightly restricted  3 Moderately restricted  4 Greatly restricted
10. Going to work?	 1 Not restricted at all  2 Slightly restricted  3 Moderately restricted  4 Greatly restricted
11. Maintaining friendship?	 1 Not restricted at all  2 Slightly restricted  3 Moderately restricted  4 Greatly restricted

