Specific Aim 2: Explore whether individual coping phenotypes predict PTG. Predictors for consideration include acute perceived stress (Perceived Stress Scale-4 [PSS-4], personality characteristics (Big Five Inventory [BFI]) coping ability (Brief COPE), social relationship quality (Social Relationship Inventory (SRI abbreviated), measures of disability in activities of daily living and instrumental activities of daily living caregiver burden (Groningen Activity Restriction [GARS] Scale), patient age and severity of illness (APACHE score).

Hypothesis 2a: ICU families coping phenotypes (stress, personality characteristics, and coping) will be associated with PTG.

Hypothesis 2b: Other variables related to the ICU (APACHE IV score, age, sex, ethnicity, whether the patient dies before follow-up) and post-ICU (care giver burden) experience will be associated with PTG at 3 mos.

Background and Significance:

Post-ICU psychological distress is common and important

The intensive care unit (ICU) is a stressful and challenging place for patients and their families, who must navigate illness and its associated discomforts as well as complex decision making in an environment characterized by tremendous uncertainty¹⁻³. Negative emotions including stress, fear, anger, and fatigue are extremely common during an ICU admission^{4,5}. Many family members experience anxiety, depression, and posttraumatic stress disorder (PTSD) during and after the ICU experience that persists years after their loved one is discharged from the ICU^{3,6-8}.

During an ICU stay, it is common for patients to be too ill to participate in decision making in the ICU⁹ – and medical decision making will generally be made by the family members designated surrogate decision makers⁷. Surrogate medical decision making may be intense and stressful and may contribute to development of anxiety, depression and posttraumatic stress disorder (PTSD) in family members³.

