4 Month Follow-up

Four months after the writing exercise, participants will be contacted to complete an instrument battery by telephone. Follow-up measures include IES-R, HADS, PSS-4, Groningen Activities Restriction Scale (GARS) for assessing impact of the traumatic event on functional and emotional health and Posttraumatic Growth Inventory (PTGI). Following participation participants will receive gift card payment in the mail.

4 Month Follow-up			
Hospital Depression and Anxiety Scale	depression and anxiety	14 items (7 each for anxiety and depression). Items scored 0 to 3. Total	Scores of 8 or higher indicate symptoms or depression or anxiety. ³³
Impact of Event Scale Revised (IES-R)	Screens for PTSD	22-item scale measuring intrusion, avoidance and hyperarousal	A mean score of ≥ 1.6 indicates PTSD symptoms. ^{34,35}
Perceived Stress Scale	Feelings of stress	4 items with scores that range from 0 to 4	Higher scores indicate greater stress. ^{36,37}
Brief COPE	Coping with stress	14 dimensions with 2 questions per dimension	Higher scores indicated greater use of a given coping strategy. ³⁸
Post-Traumatic Growth Inventory	Positive perceptions of change following a traumatic event	21 items that use a 6 point Likert scale (0-5)	Higher Scores Indicate greater PTG
Physical Symptoms Inventory – 13 Item Version	Examines physical symptoms experienced during previous 30 days adapted to include medical utilization	13 items that use a 5 point Likert Scale (1-5)	Higher scores indicate more symptoms on more days. ^{21,24}

Groningen Activity Restriction Scale (GARS)	Assess degree of restriction experienced due to providing care in 11 categories: caring for him/herself, caring for others, eating habits, shopping for him/herself, visiting friends, working on hobbies, sports and recreation, going to work, and maintaining friendship. Developed and used in ICU populations, ⁴⁶⁻⁴⁹ shopping for him/herself, visiting friends, working on hobbies, sports and recreation, going to work, and maintaining friendship. and used in ICU populations. ⁴⁶⁻⁴⁹	11 items scored from 1 to 4	Scores range from 11 to 44 with higher scores indicating greater activity restriction.

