 - Baseline terminal illness (congestive heart failure, ESRD, liver failure, cancer)

- Study Participant information:
 - Age
 - Sex
 - Race
 - Ethnicity
 - Religion (importance, affiliation, and degree of importance)
 - Employment status
 - Number of hours weekly spent with the patient (averaged over the last month) and whether the participant lives with the patient,
 - Highest level of education.
 - Limited medical history: diagnosed depression, anxiety, sleep disorder, obesity. ^{30,31}
 - Psychiatric history of depression or anxiety
 - History of substance and alcohol abuse

The informed consent form describes the elements of PHI that will be used as a part of this study. All identifiable study information that is collected will be kept on computers owned and secured by Intermountain Healthcare. Any PHI collected for this study will be de-identified prior to disclosure to study collaborators outside of Intermountain Healthcare and only under authorization of current, valid data use agreements. The code used to de-identify these subjects will be retained by the Intermountain Healthcare Principal Investigator to allow re-identification of the subject should clarification of information be required. Identifiers of study participants will be maintained securely in order to report study results to participants, e.g., via newsletters.

We will randomize family members to receive either the PTG intervention and or non-intervention control group (control writing condition). The intervention group will participate in a brief expressive writing intervention. The control group will receive a control writing condition (fact-based writing) and complete the other study measures.

Descriptive statistics will be calculated for all demographic variables as well as all instruments (both at baseline and 4 month follow up). PTGI at 4 months (along with the secondary outcomes) will be compared between the intervention and control arms using Wilcoxon Rank Sum tests. Further, we will use linear regression to assess the relationship between expressive writing and PTGI at 4 months, adjusting for other relevant factors (i.e., participant demographics, (including age), patient demographics, illness severity of the patient, social support of the participant, caregiver burden, etc.).

Sample Size:

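### The caregiver-burden form asks about care now being given, so participants whose patient has died get a missing or uninterpretable score in Hypothesis 2b and the adjusted PTGI regression

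*Protocol*

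**What the plan says.** - **The form.** The Activity Restriction Scale in Protocol Appendix 4 asks "how much you have restricted your activities in each of the following areas due to the care you are providing to your loved one". Each of its 11 items has four answers, the lowest being "Not restricted at all" (1) and the highest 4. No not-applicable answer, recall period or skip rule is printed.
- **When it is used.** The 4 Month Follow-up table gives the purpose as "Assess degree of restriction experienced due to providing care in 11 categories" and the scoring as "Scores range from 11 to 44 with higher scores indicating greater activity restriction". The battery does not differ by the patient's vital status. Burden is not among the enrolment questionnaires in Table 1, so no earlier score exists.
- **Who is asked.** The exclusion criteria remove hospice admissions, but nothing withdraws a participant whose patient later dies. Data Collection records the patient's death from the participant's own report.
- **How it is analysed.** Hypothesis 2b states that "whether the patient dies before follow-up) and post-ICU (care giver burden) experience will be associated with PTG". The analysis paragraph before Sample Size adjusts the 4-month PTGI regression for factors that end with "social support of the participant, caregiver burden, etc". That list does not name patient death.

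**The concern.** A relative whose patient has died is no longer giving care, so the question has no defined answer for that person. The likely results are a blank, or the lowest answer on all 11 items. The protocol expects such participants, because it makes patient death a predictor of PTG, and in the same hypothesis it makes burden a predictor as well.

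What is at stake is the reading of both predictors in Aim 2 and the set of participants who contribute to the adjusted PTGI regression. A blank can remove the bereaved from any model that contains burden. A floor score puts them in the same place on the scale as active caregivers who feel no restriction.

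**Working it through.** **1. Which form is the burden measure.** Eleven items scored 1 to 4 give 11 × 1 = 11 to 11 × 4 = 44, which matches the follow-up table. Appendix 4 also prints an 18-item form titled GARS, whose range would be 18 × 1 = 18 to 18 × 4 = 72. That form concerns the respondent's own daily function. The 11-item form therefore fits the table, although Aim 2 and the table both call the measure GARS.

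**2. The protocol's sample size.** Sample Size gives PTGI 45 (control) and 56 (intervention). I read the attached figures 18 and 21 as SDs. Power is not stated; I assume 80% and two-sided alpha 0.05.
- Pooled SD = √[(18² + 21²)/2] = 19.56.
- Normal formula: n per arm = 2 × [19.56 × (1.960 + 0.842)/11]² = 49.6, so 50 per arm and 100 in total.
- A t-test needs 50.6, so 51 per arm and 102 in total. Dividing the normal result by the Wilcoxon efficiency of 0.955 gives 104.

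The stated 102 is reproduced and is not in dispute.

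**3. If the bereaved leave the form blank.** A complete-case model containing burden keeps only relatives of living patients. In a joint model, death then takes one value and its effect cannot be estimated. In the adjusted PTGI regression the arm comparison continues with fewer people. The protocol gives no mortality, so the rates below are assumptions. Power is for the 11-point difference by normal approximation, with no gain from covariates; it is about 81% with all 102.

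| Assumed mortality | Bereaved of 102 | Remaining | Power |
|---|---|---|---|
| 10% | 10 | 92 | 77% |
| 20% | 20 | 82 | 72% |
| 30% | 31 | 71 | 66% |
| 40% | 41 | 61 | 59% |

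**4. If the bereaved score 11 and the model has no death term.** Assume burden among relatives of living patients has mean 20 and SD 7, mean PTGI differs by Δ in the bereaved, and burden has no true effect among the living. With p the proportion bereaved:

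slope = p(1 − p)(11 − 20)Δ / [(1 − p) × 7² + p(1 − p)(11 − 20)²]

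For p = 0.3 and Δ = +10: (0.21 × −9 × 10)/(0.7 × 49 + 0.21 × 81) = −18.9/51.3 = −0.37 PTGI points per burden point. Over the 33-point range this is −12.2 points, but the top of the scale lies (44 − 20)/7 = 3.4 SD above the assumed mean, so that figure is an extrapolation. For p = 0.4 and Δ = +10: −21.6/48.8 = −0.44. The sign reverses with Δ = −10, so over 10% to 40% mortality and Δ from +10 to −10 the slope runs from −0.44 to +0.44. It is zero if Δ = 0.

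**5. If the bereaved score 11 and the model has both terms.** Burden is constant among the bereaved, so the burden slope b comes only from relatives of living patients and is valid for them. The death coefficient is Δ − b(11 − 20). With b = 0 and Δ = +10 it is 10. With b = −0.3 it is 10 − (−0.3)(−9) = 7.3: a comparison with relatives of living patients at burden 11, no longer the overall difference of 10. With survivor burden simulated as above and truncated to 11–44, death and burden correlate at −0.42 to −0.68 for 10% to 40% mortality (variance inflation 1.2 to 1.8). The two terms overlap but can be separated.

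**The case against.** A reader might infer that Hypothesis 2b cannot be answered for both predictors at all. The documents do not support that. Hypothesis 2b does not say that death and burden enter one model, and step 5 shows that a model with both terms gives a correct burden slope among the living if the bereaved all score 11. The −0.37 slope needs death to be left out, although Hypothesis 2b names it. The loss of the death effect needs both a joint model and complete-case deletion, and the protocol states neither.

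Model form and missing-data handling commonly sit in a SAP, which is not at hand. The planned report of the patient's death would let an analyst separate the bereaved later. The primary comparison is an unadjusted Wilcoxon test and does not use burden. In the adjusted regression a floor score in both arms distorts the burden coefficient but does not by itself bias the arm comparison. Participants may also decline a question, or answer from memory of care given before the death.

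All of this limits the point, but it does not remove it. The stem, the answer set and the undifferentiated battery are fixed in the protocol, and a later plan cannot give a defined meaning to answers already collected. Answers from memory would add a third kind of score, with no recall period. The covariate list, illustrative as it is, names burden and not death.

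**Conclusion.** The point holds as a defect in how burden is measured and used for the bereaved. It affects exploratory Aim 2 and the precision of the adjusted PTGI regression. It does not touch the primary Wilcoxon comparison, and it does not make Hypothesis 2b unanswerable.

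The size cannot be fixed from the protocol, because it depends on mortality and on the PTGI difference in the bereaved, and neither is given. The head-counts and power figures rest on assumed mortality and, for power, on complete-case analysis. The slopes rest in addition on the assumed burden distribution and PTGI difference, and could have either sign or be zero. The conclusion also takes the 11-item form as the burden measure, which the scoring range supports but the naming leaves open.

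**What to change.** 1. Ask the patient's vital status at the start of the follow-up call. If the patient has died, skip the burden form and code it not applicable, separately from missing and never as 11.
2. For Hypothesis 2b, test patient death in all participants in a model without burden, and test burden only among relatives of living patients.
3. Do not let burden remove bereaved participants from the adjusted treatment-effect regression. Either leave burden out of that model, or include a death term and count burden only where the patient is alive.
4. State whether the 18-item GARS or the 11-item Activity Restriction Scale in Appendix 4 is the burden measure, and use one name throughout.

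The cost is a skip rule in the call script and a short change to the analysis text; the patient's death is already to be reported by the participant. The downside is that the burden association is estimated in fewer participants, but the scores given up had no defined meaning.
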